4.1.2. Part 2: Expansion Cohorts

Part 2 (Dose Expansion) will start after the RP2D is determined in Part 1.

The intention of Part 2 is to (i) collect additional information on the safety and PK/PD characteristics of GSK3368715 and (ii) to evaluate the clinical activity of GSK3368715 in selected disease populations.

Part 2 will consist of two expansion cohorts:

- **Expansion Cohort 2A:** Up to 36 participants with DLBCL will be enrolled. Based on the assumed prevalence of MTAP deletions, it is expected that ~ 23 % of participants (or ~ 8 out of 36 participants) will present with DLBL deficient of MTAP.

For DLBCL cohort (Part 2A), this cohort will be evaluated separately from the solid tumor cohorts (Part 2B). A Bayesian adaptive design based on hierarchical model will be used to allow interim monitoring of the response rate and allow information borrowing between the MTAP defined subgroups within the cohort. The interim futility analysis will be performed every 2-3 months with minimum of 5 additional evaluable participants from the entire cohort. The first interim futility analysis will be performed when at least 5 participants become evaluable from each of the MTAP defined subgroups. Data from both subgroups will be included in the analysis to form the Bayesian hierarchical model. Any subgroup with posterior probability of ORR > 10% sufficiently low (<20%) will be declared as ineffective and terminated for enrollment according to the design.

- **Expansion Cohort 2B:** Up to 105 participants with pancreas cancer, NSCLC, and bladder cancer, will be enrolled. The number of participants with a specific tumor histology in this cohort will is not fixed but will ultimately not exceed 35 participants of any specific tumor histology.

The three tumor histologies were selected on the basis of the higher frequency of MTAP deletions which is assumed to be ~ 30% in pancreatic cancer, ~27-32% in bladder cancer, and ~9-28% in NSCLC.

A Bayesian adaptive design based on hierarchical model will be used to allow interim monitoring of the response rate in this expansion cohort on ongoing basis. The design will also allow information borrowing across the three different histologies as well as between the MTAP defined subgroups within each histology. Participants enrolled in Part 1 who were treated at the RP2D of GSK3368715 and have the same disease histology as required for Expansion Cohort 2B will be included in the analyses as appropriate.

The first interim futility analysis will be performed when at least 5 participants become evaluable from MTAP proficient subgroup within any cohort. Data from all participants across all tumor types in part 2B will be included in the analysis to form the Bayesian hierarchical model. Details about the futility rules are specified in Section 9.4.2.1.

MTAP-Testing for Expansion Cohort 2A and -2B: Homozygous deletion of the tumor suppressor protein p16 (CDKN2A) on chromosome 9p21 is prevalent in cancer (in ~ 15-40% of all cancers) and commonly (in more than 90% of instances [[Huang, 2009](#); [Kirovski, 2011](#); [Su, 2014](#)]) involves co-deletion of the adjacent gene for MTAP.

Because of the high frequency and prognostic relevance, molecular testing for p16 (CDKN2A)-deletion is commonly conducted and p16 is a marker present on most molecular panels. Local molecular testing for p16 (CDKN2A) deletion will be utilized to prospectively stratify the Part 2 population; and will be followed by retrospective central confirmatory MTAP-deletion testing.

It is expected that participants whose tumor harbors an MTAP-deletion or wild-type MTAP are equally represented in the 2 expansion cohorts. In expansion cohorts, the intention is to stratify enrollment such that approximately 50% of participants within each of the three solid tumor types and the DLBCL cohort have an MTAP deletion.

In order to achieve the expected number of participants whose tumor harbors a MTAP-deletion, prospective MTAP testing may be implemented if the local p16 (CDKN2A) testing does not deliver the required number of enriched participants in concordance with the retrospective MTAP testing.

4.1.3. Dose-Limiting Toxicity

All toxicities will be graded using National Cancer Institute – Common Toxicity Criteria for Adverse Events (NCI-CTCAE), version 5.

An AE is considered to be a dose-limiting toxicity (DLT) if the event is considered by the investigator to be clinically relevant and attributed (definitely, probably or possibly) to the study intervention during the first 21 days of intervention and meets at least one of the criteria listed in [Table 6](#).

In addition, there are clear VTE DLT criteria:

- Upon re-initiation of enrolment under Protocol Amendment 3, any cohort in Part 1 with two (2) grade 2 venous thromboembolism (VTE) that requires systemic anticoagulation or \geq grade 3 VTE in up to 6 participants will be considered not cleared and enrolment at this dose level and higher dose levels will be permanently stopped.
- Upon re-initiation of enrolment under Protocol Amendment 3, any cohort in Part 1 with ≥ 3 grade 2 venous thromboembolism (VTE) that requires systemic anticoagulation or Grade ≥ 3 VTEs out of up to 10 participants will be considered not cleared and enrolment at this dose level and higher dose levels will be permanently stopped.
- Upon re-initiation of enrolment under Protocol Amendment 3 at 100mg, dose escalation steps will be considered in maximal steps of 50 mg depending on the pharmacodynamic effects and the safety profile observed in previous cohorts, taking into consideration the updated DLT criteria (see [Table 6](#)).
- Grade 2 venous thromboembolism (VTE) that requires systemic anticoagulation or \geq grade 3 VTE, regardless of investigator assessed causality, will be considered a DLT during the first 8 (± 1) weeks or until study discontinuation (e.g., disease progression), whichever occurs sooner.
- An end of treatment CT image is required if the participant withdraws before the end of the VTE DLT observation period ([Table 6](#)).

If an AE is considered related to the underlying disease it is not defined as a DLT.

Table 6 Dose-Limiting Toxicity Criteria

DLT criteria for Non-hematologic Toxicity	
AST or ALT	
 • Grade 3 • Grade 4 • ALT \geq 5xULN • ALT \geq 3xULN persists for \geq 4 weeks • ALT \geq 3xULN and bilirubin \geq 2xULN (>35% direct bilirubin) • ALT \geq 3xULN and INR >1.5, if INR measured • ALT \geq 3xULN associated with symptoms (new or worsening) believed to be related to liver injury or hypersensitivity
Nausea	
 • Grade 3 persisting >3 days despite BSC^a
Vomiting	
 • Grade 3 or 4 persisting > 3 days despite BSC^a
Diarrhea	
 • Grade 3 or 4 persisting > 3 days despite BSC^a
Fatigue	
 • Grade 3 persisting > 5 days
Hypertension	
 • Grade 3 that cannot be controlled with medical therapy • Grade 4
ECG-change	
 • > 20 msec extension of the QRS-interval compared to baseline
Laboratory abnormality	
 • Grade 3 persisting > 3 days despite BSC^a • Grade 4
Any other	
 • Grade 2 leading to frequent dose interruptions despite BSC^a and limiting GSK3368715 dosing to <80% of expected dose • Grade 2 requiring delay of GSK3368715 administration for > 14 days • Grade \geq3

DLT criteria for Hematologic Toxicity	
Neutropenia	
 Grade 3 persisting > 3 days despite BSC^a Febrile neutropenia Grade 4
Thrombocytopenia	
 Grade 3 persisting > 3 days despite BSC^a Grade 3 associated with clinically significant hemorrhage Grade 4
Any other ^b	
 Grade 2 and 3 leading to frequent dose interruptions despite BSC^a and limiting GSK3368715 dosing to < 80% of expected dose Grade 3 persisting > 3 days despite BSC^a Grade 4
Venous Thromboembolism	
 Grade 2 venous thromboembolism (VTE) that requires systemic anticoagulation or VTE Grade ≥ 3 during the first 8 (± 1) weeks or until study discontinuation (e.g., disease progression), whichever occurs sooner.

ALT=alanine aminotransferase; AST=aspartate aminotransferase; BSC=best supportive care; DLT=dose-limiting toxicity; ECG=electrocardiogram; ULN=upper limit of normal

- a. Best supportive care if available, according to institutional standards
b. With the exception of lymphocytopenia

For participants who experience a toxicity that meets the criteria of DLT, administration of GSK3368715 will be held pending management and resolution of the toxicity.

Participants who withdraw from the study before completing 21 days of intervention for reasons other than DLT may be replaced at the discretion of the sponsor.

Guidance for the management of toxicity, including dose modification algorithms, is provided in [Appendix 12](#).

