4.1.1. Part 1: Dose-Escalation Phase

Cohort Size: The initial dose cohort(s) will include up to three participants per GSK3368715 dose level. Cohorts will be expanded at the first instance of a \geq Grade 2 drug-related non-hematological toxicity. From there on, a minimum of 3 and a maximum of 12 DLT evaluable participants may be assigned to any single dose at the discretion of the Dose Escalation Committee (DEC) as outlined in the Dose Escalation Plan.

Replacement: If a participant fails to receive at least 75% of the planned doses within the 21-day DLT observation period for reasons other than toxicity (e.g., concurrent illness or disease progression), the participant will be replaced by additional participant(s) assigned to the same dose level and will not be counted as DLT evaluable.

Dose Escalation: After each dose cohort, a dosing recommendation for the next cohort will be made using the Neuenschwander Continual Reassessment Method (N-CRM) [[Neuenschwander, 2008](#)].

The N-CRM design makes use of a Bayesian logistic regression model relating dose and toxicity and is expected to locate the target dose level efficiently while minimizing the number of participants exposed to pharmacologically inactive or unsafe dose levels. The N-CRM method is fully adaptive and makes use of all DLT information, therefore is expected to locate the target dose level efficiently.

The N-CRM estimates, for each potential dose, the posterior probabilities that the DLT rate lies in each of four toxicity ranges:

- A dose falls in the **Under-dosing** range if the probability of a DLT at the dose is, 16%.
- A dose falls in the **Target** Toxicity range if the probability of a DLT at the dose is $\geq 16\%$ and $< 33\%$.
- A dose falls in the **Excessive** Toxicity range if the probability of a DLT at the dose is $\geq 33\%$, and $< 60\%$.
- A dose falls in the **Unacceptable** Toxicity range if the probability of a DLT at the dose is $\geq 60\%$

At the time of each dose-escalation decision, the dose with the highest posterior probability of lying in the Target Toxicity range will be the model-recommended dose for

the next cohort. Additionally, the following constraints for the recommended dose will be maintained:

- The posterior probability of the DLT rate lying in the Excessive Toxicity or Unacceptable Toxicity range is less than 25%.
- VTE safety rules

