 - Upon re-initiation of enrolment under Protocol Amendment 3, details of a VTE meeting the DLT criteria are given in Section 4.1.3 and in Table 6.
- Upon re-initiation of enrolment under Protocol Amendment 3 at 100mg , dose escalation steps will be considered in maximal steps of 50 mg, depending on the pharmacodynamic effects and the safety profile observed in previous cohorts, taking into consideration the updated DLT criteria (see Table 6).
- *Note:* GSK3368715 dose de-escalation is also possible using this method.

An updated posterior estimate of the dose-toxicity curve will also be provided at the time of the dose-escalation meeting. Further details about the N-CRM approach are provided in Section 9. Although the N-CRM will be used to recommend the next dosing level, the DEC (i) will review all available data, including safety, PK and PD data from current and prior cohorts, (ii) can halt or reduce the GSK3368715 dose based on clinical judgement at any time during the trial, and (iii) can recommend alternative schedule(s) if emerging data suggest that continuous daily dosing will result in excessive toxicity or limited efficacy (Section 4.1.4). *Note:* if an alternative schedule is evaluated, the starting dose at the time of a schedule change will be the dose for which the target toxicity level was not exceeded using once daily dosing schedule.

Dose Schedule: GSK3368715 will be dosed initially orally (po) Based on emerging safety-, PK-, and PD- data, the DEC may recommend to evaluate alternative dosing schedule(s). The starting dose for an alternative dosing schedule will not exceed the highest GSK3368715 dose declared safe by the DEC at the time of the proposed schedule change.

During dose escalation, the first dose will be staggered by at least 24 hours between the participants enrolled within a cohort. This staggered dosing start is not required for participants enrolling at previously cleared doses.

PK/PD/Metabolite/Biomarker-Cohort: At GSK3368715 dose levels near to the expected RP2D, the DEC may recommend to expand a cohort(s) to up to 12 participants for additional PK- and PD-, metabolite- and/or biomarker-sample collection.

Under protocol amendment 03, a 100mg PK/PD cohort will be opened on resuming enrolment, and a 50mg PK/PD cohort may be opened in parallel. An additional PK/PD cohort may be opened later at a different dose level. The total maximal number of participants enrolled on PK/PD cohorts will be approximately 30.

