4.1.4. Dose Escalation Committee

The Dose Escalation Committee (DEC) will be established by GSK to monitor intervention-emergent data on an ongoing basis throughout study conduct for the purpose of ensuring the continued safety of participants enrolled in this study. The DEC will be chaired by the GSK medical monitor and membership will include a GSK scientist, GSK pharmacovigilance physician, GSK statistician, GSK pharmacologist, along with additional GSK staff as appropriate and all participating investigators.

In Part 1, the DEC will review relevant safety, PK, and PD data generated immediately after all participants treated in the same dose cohort have passed the DLT period, as defined in the Dose Escalation Plan. Although the escalation of the GSK3368715 dose will be guided by the N-CRM, the DEC can override this recommendation.

In Part 2, the members from the DEC will continue to routinely assess cumulative safety data as a safety evaluation team. This team may decide to stop further enrolment if intervention-emergent toxicity is determined to result in an unfavourable change in participant risk/benefit.

In addition, throughout the conduct of the study the DEC may decide to:

1. Modify the dose escalation of GSK3368715 proposed by the N-CRM based on clinical judgement. *Note:* GSK3368715 dose steps will not exceed 50 mg dose increments under protocol amendment 03.
2. Investigate alternative dosing regimens
3. Modify the timing, frequency, and/or type of safety assessments performed during study conduct
4. Request intervention of additional participants at previously completed dose levels for the purpose of obtaining additional safety, PK, PD, metabolite, or biomarker data (i.e. PK/PD/Metabolite/Biomarker-Cohort).
5. Recommend intra-participant dose escalation allowing participants to be moved from a lower to a higher GSK3368715 dose, not exceeding the MTD if the DEC has declared the next dose cohort as safe
6. Decide on intervention beyond initial evidence of disease progression in participants who receive clinical benefit (i.e., stable Eastern Cooperative Oncology Group or ECOG performance status and no clinical symptoms indicative of rapid disease progression)
7. Increase the size of an expansion cohort or recommend to add additional expansion cohorts to further characterize the safety and efficacy profile of GSK3368715
8. Halt enrolment into any cohorts as deemed appropriate based on emerging clinical data at any time during the trial.

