9.2.1. Dose Escalation

N-CRM design is a type of Bayesian adaptive dose-escalation approach. The design classifies the DLT rate into four categories and makes dose recommendations based on posterior distribution of the four categories:

- Under-dosing: DLT rate < 16%
- Target toxicity: 16% ≤ DLT rate < 33%
- Excessive toxicity: 33% ≤ DLT rate < 60%
- Unacceptable toxicity: DLT rate ≥ 60%

At the end of DLT observation period for each dose level, the posterior distribution of DLT rate will be summarized by the posterior probability of the DLT rate falling into the interval of under-dosing, target toxicity, excessive toxicity, and unacceptable toxicity respectively. The recommended dose is the one that maximizes the probability of target toxicity while controlling the probability of excessive or unacceptable toxicity no more than 25%.

9.2.1.1. Operating characteristics of the safety stopping rule for VTE events in dose escalation

Simulations were used to evaluate the design performance of the safety stopping rules planned for the safety evaluation of VTE events during the dose escalation phase (Part 1) of this study. In these simulations, we simulate 100,000 independent trials and evaluate the performance of the model on average. In each simulation, a cohort is enrolled until either 2 or more VTE events have been observed among 6 or fewer participants or 3 or more VTE events have been observed among 7-10 participants.

[figure not shown]
[Table 8](#) details the scenarios evaluated as well as the average number of participants dosed in each cohort, and the percentage of simulated trials that completed that dose level. [Figure 4](#) graphically represents the operating characteristics of the safety stopping rules for each cohort. Each line of the plot represents a different true VTE incidence rate detailed in [Table 8](#). The scenarios considered a range from a true VTE incidence rate of 5% to a true VTE incidence rate of 30%. Note that these simulations only take VTE events into consideration, and this VTE safety stopping rule will be evaluated in addition to the traditional DLT rules within the dose escalation framework detailed in [Section 4.1.1](#).

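### The fixed VTE stopping rule and Table 8 end at 10 participants, although up to 12 are permitted at a dose or in a PK/PD cohort

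*Protocol*

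**What the plan says.** Protocol section 4.1.3 sets two fixed boundaries for any Part 1 cohort once enrolment resumes under Amendment 3. A qualifying event is a Grade 2 VTE needing systemic anticoagulation, or a VTE of Grade 3 or higher. The first boundary is two such events in up to 6 participants. The second is three or more: the cohort "out of up to 10 participants will be considered not cleared and enrolment at this dose level and higher dose levels will be permanently stopped". SAP section 2.3 repeats both.

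Section 9.2.1.1 simulates the same rule. A cohort stops at two or more events among 6 or fewer participants, or when "3 or more VTE events have been observed among 7-10 participants". Table 8 reports the resulting stopping percentages.

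The permitted sizes are larger. Section 4.1.1 states that "a minimum of 3 and a maximum of 12 DLT evaluable participants may be assigned to any single dose", and SAP 2.3 gives the same maximum. For PK/PD cohorts, section 4.1.1 adds that "the DEC may recommend to expand a cohort(s) to up to 12 participants". The planned size is smaller: section 9.2 expects about 10 per PK/PD cohort, and section 4.1.1 about 30 over all PK/PD cohorts.

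Two other safeguards apply at any size.
- A qualifying VTE, "regardless of investigator assessed causality, will be considered a DLT during the first 8" (±1) weeks, so it enters the N-CRM. That model's recommendation is constrained as follows: "The posterior probability of the DLT rate lying in the Excessive Toxicity or Unacceptable Toxicity range is less than 25" per cent.
- Under section 4.1.4 the DEC may "Halt enrolment into any cohorts as deemed appropriate based on emerging clinical data at any time during the trial".

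**The concern.** Amendment 3 added the VTE rule after enrolment had been paused for thromboembolic events. Its effect is strong: it permanently closes the dose and every higher dose. Section 9.2.1.1 says that it operates on top of the usual DLT rules, so it was not meant to be replaced by them.

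A fixed stop should cover every cohort size that the plan allows, and this one says nothing about participants 11 and 12. A cohort with two affected by number 10 could then have a third, or a third and a fourth, without triggering the permanent closure. The remaining safeguards are of another kind. On the model, section 4.1.4 says: "Although the escalation of the GSK3368715 dose will be guided by the N-CRM, the DEC can override this recommendation". The power to halt is discretionary. Table 8 would also no longer describe the cohort being run.

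**Working it through.** **Inputs.** Boundaries from sections 4.1.3 and 9.2.1.1: stop at 2 or more affected within the first 6, or 3 or more by participants 7 to 10. True incidences p and stated stopping percentages from Table 8. Maximum of 12 from section 4.1.1. Write q = 1 − p. Each participant counts once, grades are pooled as in 9.2.1.1, participants are independent, and each outcome is taken as known before the next participant is counted.

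**Step 1: reproduce Table 8.** A cohort of 10 escapes the stop only with at most 1 affected in the first 6 and at most 2 in all:
- none affected: q^10
- one affected: 10pq^9
- two affected, not both in the first 6: (6pq^5)(4pq^3) + (q^6)(6p²q²) = 30p²q^8

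P(stop by 10) = 1 − q^10 − 10pq^9 − 30p²q^8. At p = 0.20 this is 1 − 0.1074 − 0.2684 − 0.2013 = 0.4229, against 42.1% in Table 8. All six incidences agree to within 0.3 points (table below), so Table 8 describes cohorts that end at 10.

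**Step 2: the uncovered outcomes in a cohort of 12.**
- Third affected is number 11: 30p²q^8 × p = 30p³q^8.
- Third affected is number 12: two affected after 11 without a stop has probability 30p²q^9 + 10p²q^9 = 40p²q^9; multiplying by p gives 40p³q^9.
- Four of 12 with no stop (two by number 10, then both 11 and 12): 30p^4q^8. This is part of the number-11 case.

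At p = 0.20: 30 × 0.008 × 0.1678 = 4.03%; 40 × 0.008 × 0.1342 = 4.29%; sum 8.32%. Four of 12: 30 × 0.0016 × 0.1678 = 0.81%.

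| True incidence | Table 8 | Exact, to 10 | Third at no. 11 | Third at no. 12 | Sum | 4 of 12, no stop | Stop if ≥3 carried to 12 |
|---|---|---|---|---|---|---|---|
| 5% | 3.8 | 3.64 | 0.25 | 0.32 | 0.56 | 0.01 | 4.20 |
| 10% | 13.6 | 13.48 | 1.29 | 1.55 | 2.84 | 0.13 | 16.32 |
| 15% | 26.9 | 27.18 | 2.76 | 3.13 | 5.89 | 0.41 | 33.06 |
| 20% | 42.1 | 42.29 | 4.03 | 4.29 | 8.32 | 0.81 | 50.61 |
| 25% | 56.8 | 56.83 | 4.69 | 4.69 | 9.39 | 1.17 | 66.21 |
| 30% | 69.5 | 69.50 | 4.67 | 4.36 | 9.03 | 1.40 | 78.53 |

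All entries are percentages. The last column is the exact value to 10 plus the sum.

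**Step 3: would the N-CRM catch these cases?** Its prior is not given in the documents, so this is indicative only. Assume a single dose, no other DLTs, no borrowing across doses, and beta priors (0.5, 0.5), (1, 1), (0.25, 0.75), (0.5, 1.5) and (0.2, 0.8). With x affected of n, the posterior is beta(a + x, b + n − x). The posterior probability of a DLT rate of at least 33% is then:
- 3 of 11: 0.285 to 0.403
- 3 of 12: 0.225 to 0.332
- 4 of 12: 0.446 to 0.562

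The 25% limit is crossed under all five priors at 3 of 11 and 4 of 12. At 3 of 12 it depends on the prior.

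**The case against.** The rule fits the plan. Section 9.2 expects about 10 per PK/PD cohort, and the total of about 30 in section 4.1.1 matches up to three such cohorts. Rule, simulation and planned size all end at 10. The gap opens only if the DEC goes further, and the documents give no probability for that. This stands, and every percentage for participants 11 and 12 is conditional on it.

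The unit is also mixed. The VTE rule counts per cohort after enrolment resumed, whereas one of the limits of 12 is per dose. Doses of 50 and 100 mg already had participants. If those count towards the 12, a reopened cohort at either dose might never reach an eleventh new participant. The text does not settle this. A new dose level could still reach 11.

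Not stopping at 3 of 12 is defensible. That rate is 25%, below the 33% of 2 in 6 and the 30% of 3 in 10, and inside the 16–33% target range for DLTs. This stands for about half of the calculated probability (4.3 of 8.3 points at 20% incidence).

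Enrolment order is not event order. The VTE window is 8 (±1) weeks, while first doses are staggered by only 24 hours, and not at all at cleared doses. Participant 12 may be dosed before a VTE in participant 11 appears. The split between 11 and 12 is therefore only approximate.

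A reader might infer that nothing protects participants beyond the tenth. The documents do not support that: a qualifying VTE is a DLT whatever its cause, the N-CRM limit applies, and the DEC may halt. Nor do they show that the gap affected anyone. No cohort is reported to have gone past 10, and SAP 2.1 says that the DEC judged the 100 mg cohort safe. Section 4.1.1 also refers to a Dose Escalation Plan, not among the documents, which may say more.

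**Conclusion.** The concern holds as a gap in the written rule. For dose-escalation and PK/PD cohorts, the fixed stop covers up to 10 participants and the plan permits 12. Between the two, a cohort at 3 of 11 or 4 of 12 would meet no fixed boundary, although 4 of 12 equals the 33% that closes a dose at 2 of 6. The decision would pass to a model that the DEC can override and to DEC judgement.

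If a cohort reaches 12, the chance of a third affected participant first at number 11 or 12 is 0.6% at 5% true incidence, rises to 9.4% at 25%, and is 9.0% at 30%. This assumes independent participants and outcomes known in enrolment order.

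Table 8 is not wrong. It is correct for the size that it describes and simply does not extend to the permitted maximum. The point is minor, because SAP 2.1 states that no further enrolment will take place. What remains is how the rule is described, and any reuse of it.

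**What to change.** Choose one of two changes in section 4.1.3, and mirror it in SAP 2.3.

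1. Cap VTE-monitored Part 1 cohorts at 10 participants enrolled under Amendment 3. The rule and Table 8 then hold as written. The food effect cohort has a minimum of 12 (section 4.1.1.1), so say whether the rule is meant to cover it.
2. Keep the present form and extend it: stop at 2 or more affected participants in up to 6, or 3 or more affected participants in up to 12. The second tier should not be reworded to start at 7, because it now also covers six or fewer. Re-run Table 8 to 12; the exact values are 4.2, 16.3, 33.1, 50.6, 66.2 and 78.5%.

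Either way, state that the count is of affected participants, per cohort, among those enrolled under Amendment 3. A boundary of 4 at number 12 could also be defended; what matters is that one is stated.

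The cost is a phrase and, for the second option, a short re-run. Relative to ending at 10, the extension adds 0.6 points of stopping at 5% incidence (4.20 − 3.64) and 2.8 points at 10% (16.32 − 13.48).
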